7.2 ADAS-cog

The Alzheimer's Disease Assessment Scale-cognitive subscale (ADAS-cog) rating instrument (Rosen et al. 1984) will be used to evaluate global cognitive functioning, and thus AD severity. The ADAS-cog will serve a dual function as both a safety measure and an efficacy endpoint. Refer to the referenced publication for details regarding the administration and scoring of the ADAS-cog.

7.3 ADCS-ADL

The ADCS-ADL rating instrument (Galasko et al. 1997) will be used to evaluate functional capacity. The ADCS-ADL will serve a dual function as both a safety measure and an efficacy endpoint. Refer to the referenced publication for details regarding the administration and scoring of the ADCS-ADL.

7.4 NPI

The neuropsychiatric inventory (NPI) (Cummings et al. 1994) will be used to evaluate behavioral symptoms, including agitation and irritability, which are possible side effects of LEV. The NPI will serve a dual function as both a safety measure and an efficacy endpoint. Refer to the referenced publication for details regarding the administration and scoring of the NPI.

8. ASSESSMENT OF LEV BLOOD LEVELS

The steady state blood levels of LEV will be obtained for each subject on study days 1, 29, 57, and 85.

8.1 Blood Collection

Blood samples will be taken by direct venipuncture. The blood sample volume at each collection time point will be 18 mL. The samples will be collected in three 6 mL tubes coated in silica clot activator. One tube will be processed to serum and sent to Quest Diagnostics to assess serum levels of LEV and prolactin. The remaining 2 tubes will be processed to serum and stored at the UCSF Neuroscience Clinical Research Unit (NCRU) lab for future analyses.

8.2 Blood Processing, Labeling, and Shipment

Blood samples intended for Quest Diagnostics LEV and prolactin serum levels (one 6 mL tube) will be processed in the following manner, as outlined in the Quest Diagnostics lab manual. The whole blood will be allowed to clot for 60 minutes and centrifuged at 2200 – 2500 RPM for at least 15 minutes. The resulting serum will be split into 2 cryovials which will be stored at -20°C and immediately shipped for external assessment of LEV and prolactin levels. Detailed labeling and shipping instructions will be specified by Quest Diagnostics.

Blood samples intended for local storage (two 6 mL tubes) will be processed to serum in an identical manner. Each serum sample will be split into 4 – 6 cryovials (1 mL/vial) to serve as back-up samples. The serum samples will be stored at approximately -80°C until analyzed. The back-up samples will be reserved for retesting if required.

8.3 Bioanalytical Methods

The concentration of LEV in serum will be measured using validated liquid chromatography/tandem mass spectrometry (LC/MS-MS) methods.

9. ASSESSMENT OF EFFICACY

The efficacy endpoints for this trial include changes in epileptiform activity, cognition, degree of disability, and behavior. The exploratory endpoints for this trial include changes in cognition (novel tasks and subcomponents of established standardized tasks), clinical fluctuations, MEG power spectrum, MEG-I functional connectivity, blood prolactin levels, and subgroup analysis of all efficacy measures.

9.1 NIH EXAMINER

The NIH EXAMINER (Executive Abilities: Measures and Instruments for Neurobehavioral Evaluation and Research – <http://examiner.ucsf.edu>) will be used to measure executive function. The NIH EXAMINER battery of tests has psychometrically robust scales generated using item-response theory and provides strong predictors of real-world executive behavior (Possin et al. 2013). The NIH EXAMINER tasks will include antisaccade, set shifting, flanker task, dot counting, spatial 1-back, category fluency, and letter fluency. Four alternative forms will be used.

9.2 Epileptiform activity

Epileptiform activity will be measured using an overnight video-EEG and a 1-hr resting magnetoencephalography with simultaneous EEG (M/EEG). MEG-compatible EEG electrodes will be fixed to the scalp using a standard international 10-20 electrode placement. During the screening visit, each subject will undergo an overnight video-EEG, including a 3-min session of hyperventilation followed by 7 minutes of post-hyperventilation resting state activity. At the screening visit and each study visit (study days 1, 29, 57, and 85), subjects will undergo an M/EEG. The M/EEG will be recorded on a whole-head MEG system (MISL, Coquitlam, British Columbia, Canada) consisting of 275 axial gradiometers (sampling rate = 600 Hz). Three fiducial coils including the nasion and the left/right pre-auricular points will be placed to localize the position of the head relative to the sensor array. These points will later be co-registered to a T1-weighted structural magnetic resonance image (MRI) to generate a head shape. MRI scans will be acquired on a 3 Tesla Siemens MRI scanner at the UCSF Neuroscience Imaging Center. Data collection will be optimized to minimize within-session head movements to not exceed 0.5 cm. Sixty minutes of continuous EEG and MEG recording will be collected from each subject lying supine and with eyes closed. The last 10 minutes will include 3 minutes of hyperventilation followed by 7 minutes of post-hyperventilation resting state activity. Hyperventilation is a provocative maneuver that can help elicit epileptiform activity.

The overnight EEG recordings will be read by an epileptologist and the M/EEG recordings will be read by an epileptologist with specialized training in MEG. The readings will note whether there is any epileptiform activity (spikes and sharp waves), and quantify the total number of spikes and sharp waves present during the recording. The M/EEG readings will note whether epileptiform activity is present on MEG, EEG, or both. M/EEG often detects spikes not detected by EEG (Kirsch et al. 2007).

9.3 ADAS-cog

The ADAS-cog rating instrument (Rosen et al. 1984) will be used to evaluate the global cognitive functioning, and thus AD severity. The ADAS-cog is a 70-point scale that includes an assessment of verbal memory, language, orientation, reasoning, and praxis. Four alternative forms will be used. Refer to the referenced publication for details regarding the administration and scoring of the ADAS-cog. We added a 45-min recall trial to the word recall task as an exploratory measure.

9.4 Stroop Test

The Stroop Test (Stroop 1992) will be used to assess executive functions including selective attention, cognitive flexibility and processing speed. Subtasks include Stroop color naming and Stroop interference naming, and each subtask is restricted to 1 minute. Measures include color naming correct, color naming errors (uncorrected and self-corrected), interference naming correct, and interference naming errors (uncorrected and self-corrected). Subjects who are color blind will be excluded from this task.

9.5 Virtual Route Learning Test

The Virtual Route Learning Test will be used to assess navigation learning. Subjects learn a pre-determined route comprised of 15 turns through a virtual neighborhood by trial and error over a maximum of 15 trials, responding via a driving simulator. Four alternate forms with different neighborhoods and routes will be used. In each form, there is a single building repeated many times, and unique cues (e.g., distinct buildings, a bush, grass, palm trees, hot dog stand, school bus, etc.). Performance is measured by accuracy summed across trials 2 through 15 (max score = 210) and by accuracy at the delay trials (max score = 15) Additional performance metrics will be explored as described in section 10.2.

9.6 Fluctuation questionnaire

Two standardized methods will be used to quantitate fluctuations of dementia symptoms: The Clinician Assessment of Fluctuation and the One Day Fluctuation Assessment Scale (Walker et al. 2000). These scales consist of a series of questions addressed to the caregiver/informant. The Clinical Assessment of Fluctuations (range 0-12) quantifies fluctuations in confusion or consciousness over the previous month. The One Day Fluctuation Assessment Scale (range 0-21) focuses on fluctuating confusion over the day prior to the assessment and includes the following seven items: falls, fluctuations, drowsiness, attention, disorganized thinking, altered level of consciousness, and communication.

9.7 CDR-SOB

The Clinical Dementia Rating (CDR) will be used to as a global measure of dementia severity (Morris 1993). The CDR consists of questions addressed to the caregiver/informant and includes the following domains: memory, orientation, judgment and problem solving, community affairs, home and hobbies, and personal care. Scores in each domain include 0 (no impairment), 0.5 (questionable

impairment), 1 (mild impairment), 2 (moderate impairment), and 3 (severe impairment). Refer to the referenced publication for details regarding the CDR scoring rules. The CDR sum of boxes (CDR SOB) summates the severity score for all domains and provides a higher range of values for tracking changes over time (range 0-18).

9.8 ADCS-ADL

The Alzheimer's Disease Cooperative Study Activities of Daily Living Inventory (ADCS-ADL) rating instrument (Galasko et al. 1997) will be used to evaluate functional capacity. The ADCS-ADL is a caregiver rated questionnaire of 23 items. Possible scores range from 0-78, where 78 implies full functioning with no impairment. Refer to the referenced publication for details regarding the administration and scoring of the ADCS-ADL.

9.9 ADCS-CGIC

ADCS-clinical global impression of change (ADCS-CGIC) is a seven-point scale that gives a global rating of change from baseline (Schneider et al. 1997). The baseline and follow up assessments are based on interviews with the subject and the informant. Refer to the referenced publication for details regarding the administration and scoring of the ADCS-CGIC.

9.10 NPI

The neuropsychiatric inventory (NPI) (Cummings et al. 1994) will be used to evaluate behavioral symptoms. The informant is asked about the presence and severity of the following neuropsychiatric abnormalities: delusions, hallucinations, agitation/aggression, depression/dysphoria, anxiety, elation/euphoria, apathy/indifference, disinhibition, irritability/lability, motor disturbance, nighttime behaviors, and appetite/eating. Refer to the referenced publication for details regarding the administration and scoring of the NPI.

9.11 MEG spectral analysis

The power spectral density for different frequency bands will be measured via resting-state magnetoencephalography (MEG). A 60-second artifact-free recording segment from the first 10 minutes of recording (prior to sleep onset) will be manually selected for analysis. For each subject, power spectrograms of this 60-second epoch of sensor data will be generated using the power spectral density estimation based on Welch's averaged modified periodogram method of Matlab signal processing toolbox (sampling rate of 600 Hz). In subjects who are able to complete additional tests, we will measure dynamics of neural responses during cognitive tasks such as speech preparation and execution.

9.12 MEG-I

Whole-brain alpha-band functional connectivity will be derived from MEG-imaging (MEG-I) using the 60-second artifact-free recording epoch that is selected for the MEG spectral analysis. MEG-I uses MEG sensor data with millisecond precision and applies source reconstruction algorithms to

overlay cortical oscillatory activity onto structural brain images. Source-space MEG-I reconstructions and functional connectivity metrics will be computed with the NUTMEG software suite (<http://nutmeg.berkeley.edu>). We will compute imaginary coherence, which is a reliable metric for functional connectivity with MEG reconstruction. Functional connectivity will measure the strength of coherence between a given region and the rest of the brain. We will perform an unbiased search for MEGI-functional connectivity deficits that correlate with specific cognitive, behavioral, and functional deficits. Refer to the referenced publication for details of the methodology (Hinkley et al. 2011).

9.13 Prolactin levels

Blood samples intended for Quest Diagnostics LEV and prolactin serum levels (one 6 mL tube) will be processed in the following manner, as outlined in the Quest Diagnostics lab manual. The whole blood will be allowed to clot for 60 minutes and centrifuged at 2200 – 2500 RPM for at least 15 minutes. The resulting serum will be split into 2 cryovials which will be stored at -20°C and immediately shipped for external assessment of LEV and prolactin levels. Prolactin will be assessed via immunoassay.

Blood prolactin levels have been reported to be elevated in epileptic patients with interictal epileptiform discharges during awake states compared to nonepileptic control subjects (Molaie et al. 1986). We will explore whether prolactin levels correlate with epileptiform activity in our subjects and whether prolactin levels are reduced by LEV administration compared to placebo.

10. STATISTICS

10.1 Sample Size Considerations

We based sample-size estimates on our hypotheses that LEV will improve cognitive performance to an extent that is clinically meaningful, compared to placebo. Standard sample-size calculations for repeated measures analysis of variance (ANOVA) (Cohen 1988) show that F tests could detect an effect size of 0.356 with power greater than 0.8 with our sample sizes, allowing for a 10% dropout rate.

For the M/EEG exams, if we observe epileptiform activity in 12 of our subjects (33%), as predicted by our preliminary data, we should be powered to detect small reductions in epileptiform activity during LEV treatment compared to placebo. As a reference, 10 hAPP mice provided robust power to detect a 40% reduction ($p<0.0005$) in spike frequency with chronic LEV administration compared to baseline (Sanchez et al. 2012).

10.2 Statistical Analysis of Efficacy Data

Data from all subjects who complete at least the first 4 weeks of the study drug (placebo or active) will be included in the efficacy analysis. Subjects whose biomarkers (CSF or amyloid PET) are found to be unsupportive of AD after they enroll in the trial will be excluded from the efficacy analysis.

Cognitive, behavioral and functional measures, as well as M/EEG epileptiform activity, power spectral density for different frequency bands, neural activity during cognitive tasks, and MEG-I functional connectivity at study days 1, 29, 57, and 85 will be recorded and summarized. Descriptive statistics will be generated as appropriate (i.e., mean, median, range, and standard deviation for continuous data and frequency for categorical data).

Each treatment effect will be tested for the assumption of normality. If the data are not normally distributed, we will investigate transforming data so they are normally distributed or nonparametric options. If we choose parametric tests, significance testing will be performed using ANOVA for repeated measures with drug treatment (LEV or placebo) as the independent variable. Prior to this analysis, ANOVA will be used to analyze the effect of drug-placebo sequence and to compare group demographics and severity of dementia at baseline (MMSE and CDR-SOB); if any of these factors confound the relationship between the study drug and the outcome measure, then they will be included as covariates in the ANOVA model. If factors arise that limit the appropriateness of the repeated-measures ANOVA model, such as a large dropout rate or varying data collection time points causing imbalance of longitudinal data, we will substitute a linear mixed effects regression model to better fit the longitudinal data without the intrinsic constraints of the repeated-measures ANOVA framework (Fitzmaurice et al. 2004, Finucane et al. 2007). If a drug carryover effect is observed on an outcome measure between weeks 4 and 8, then we will analyze the initial 4 weeks of the study separately for this outcome measure. Analyses will be two-tailed except for analysis of epileptiform activity, which will be one-tailed based on our expectation that LEV will reduce

epileptiform activity (Sanchez et al. 2012, Mintz et al. 2009). For all analyses, the null hypotheses will be rejected at $p < 0.05$.

For the Virtual Route Learning Task, we will measure total accuracy summed across trials 2 through 15 (max score = 210) and accuracy at the delay trials (max score = 15). We will also explore the trial-by-trial accuracy, error rates, learning rates and asymptotes. The preliminary data suggest a 2 parameter exponential model will provide a good fit for the learning data. We will compare estimated learning rates and asymptotes parameters using ANOVA for repeated measures with drug treatment (LEV or placebo) as the independent variable. However, if additional data collection suggests that simple slopes better summarize the data, then we will use linear mixed effects models. If we use linear mixed effects models and residuals are not normally distributed, we will use bootstrapping techniques to produce reliable standard errors.

For the whole-brain MEG-I functional connectivity analyses, neuropsychological, behavioral, and functional measures from each subject will be correlated with global connectivity values at each voxel using the Pearson's correlation. Corrections for multiple comparisons will be performed using a cluster correction with a cutoff level of 20 voxels, and p values thresholded to 0.01. If no significant voxels are found at this threshold, we will use a less stringent threshold of $p < 0.05$. A hierarchical validation analysis will be used to account for multiple cognitive, behavioral, and functional tests.

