3. STUDY DESIGN

This is a phase 2a, single-center, randomized, double-blinded, placebo-controlled, crossover study of the efficacy of LEV in patients with AD. We will enroll 36 subjects. Each subject will undergo a screening assessment, including a neuropsychological battery, caregiver interview, an overnight video-EEG including hyperventilation, a 1-hr magnetoencephalography with simultaneous EEG (M/EEG) including hyperventilation, and blood test. For patients with known seizures or subclinical epileptiform activity, the video-EEG and M/EEG will be optional. Cerebrospinal fluid (CSF) will be obtained to assess beta-amyloid ($A\beta$) peptide and tau protein levels in subjects in whom positron emission tomography (PET) amyloid imaging is not already completed or scheduled. Subjects who are consented to enroll in the treatment trial will be randomized into two groups and treated in a double-blinded design. One group will receive low-dose LEV treatment (125 mg b.i.d.) for 4 weeks, followed by washout for 4 weeks, and then placebo treatment (b.i.d) for 4 weeks, while the other group will receive these treatments in reverse sequence. At weeks 0, 4, 8, and 12, participants will undergo a 1-hr M/EEG including hyperventilation, a neuropsychological battery and caregiver interview, and serum LEV and prolactin levels.

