4.3 Withdrawal of Subjects

A subject may choose to withdraw from this study at any time for any reason without penalty of jeopardizing their health care or loss of benefits to which the subject is otherwise entitled.

A subject will be withdrawn from this study if one or more of the following events occur:

1. Subject requests to be withdrawn from study;
2. AE that in the judgment of the Investigator poses unacceptable risk to the subject;
3. Intercurrent illness, including seizure, that requires treatment that is not consistent with the protocol requirements, or intercurrent illness or the associated treatment that in the judgment of the Investigator poses a significant risk to the subject for continued participation in the study;
4. Pregnant or suspected of being pregnant;
5. Use of prohibited medication (listed in Section 5.7) that in the judgment of the Investigator will interfere with the interpretation of the results of this study;
6. Significant protocol violation or noncompliance on the part of the subject or the Investigator;
7. Investigator terminates the study;
8. Any other reason that in the judgment of Investigator poses unacceptable risk to the subject.

If a subject is withdrawn from the study, the date and reason will be recorded in the source documents, and final study visit evaluations will be performed if feasible. Any subject withdrawn due to a suspected study drug-related adverse event (AE) would be followed until resolution or

stabilization of the event.

If subject becomes pregnant or is suspected of being pregnant, study drug will be discontinued immediately, and the subject will be referred to an obstetrician/gynecologist experienced in reproductive toxicity for further evaluation and counseling. The subject will be followed until delivery or other termination of pregnancy for outcome.

Subjects may choose to withdraw authorization to use and disclose their Protected Health Information (PHI) as defined by the Health Insurance Portability and Accountability Act (HIPAA) of 1996 or foreign equivalent where appropriate. Such withdrawal of authorization must be made to the Investigator in writing. Any PHI collected by the Investigator prior to the date of such withdrawal will continue to be used and disclosed.

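### The efficacy set is conditioned on completing four weeks of study drug, and the default ANOVA gains nothing from period-1-only subjects; the effect is modest but cheap to remove

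*Combined protocol and SAP*

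**What the plan says.** Section 3 sets the size: "We will enroll 36 subjects". Section 6.3 places randomisation at the end of Day 1, with the first dose that evening.

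Section 10.2 then fixes who enters the efficacy analysis: "Data from all subjects who complete at least the first 4 weeks of the study drug (placebo or active) will be included". The synopsis has the same rule. Section 10.2 also removes subjects whose biomarkers turn out not to support AD. That is a separate rule and is not the subject of this point.

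Section 4.3 lists adverse events and intercurrent illness, including seizure, among the reasons for withdrawal. It adds that at withdrawal "final study visit evaluations will be performed if feasible".

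The parametric default in section 10.2 is repeated-measures ANOVA with treatment as the independent variable. If dropout is large or the data become unbalanced, "we will substitute a linear mixed effects regression model". No figure says what counts as large. If carryover is observed for an outcome, the first 4 weeks are analysed separately for it.

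Section 10.1 gives the power claim: "F tests could detect an effect size of 0.356 with power greater than 0.8 with our sample sizes, allowing for a 10% dropout rate". No all-randomised set, missing-data assumption or missing-data sensitivity analysis is given.

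**The concern.** Two things happen after randomisation that the plan does not control.

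First, a subject enters the efficacy set only by finishing 4 weeks of the assigned treatment. Because an adverse event is a withdrawal reason, finishing can depend on treatment. If those who stop early are those who do badly on LEV, the remaining LEV scores look better than they should. The criterion is drug completion rather than availability of data, so an evaluation obtained at an early withdrawal is left out even when it exists.

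Second, the rule admits subjects who have only period 1, but the default test cannot use them. A within-subject treatment contrast needs a score under each treatment. The mixed model can use one-period subjects, but its trigger is undefined, so the model for the primary NIH EXAMINER test is settled once dropout is known.

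At stake are the comparability that randomisation provides, a small amount of precision, and full pre-specification of the primary test.

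**Working it through.** **Inputs.** From the plan: 36 subjects, hence 18 per sequence; 10% dropout, so 36 × 0.9 = 32.4, taken as 32 with both periods; effect size 0.356; two-sided 5% for the primary endpoint. Assumed, because the plan does not give them: within-subject correlation ρ from 0.3 to 0.8, and who leaves.

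**1. The plan's own figure.** Read 0.356 as Cohen's f, with 32 × 2 = 64 observations treated as independent. Then λ = 0.356² × 64 = 8.11 on 1 and 62 degrees of freedom, and power is 0.801. The f detectable at 80% power is 0.3557, so the figure reproduces. The sample size therefore already rests on about 32 subjects with both periods. The same formula gives 0.846 with 36, 0.774 with 30 and 0.744 with 28.

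**2. Precision lost by not using period-1-only subjects.** Suppose all 4 dropouts (36 − 32) come after Day 29, two per sequence. Each sequence then has n = 18 in period 1 and m = 16 with both periods. For a model with treatment, period and sequence, the variance relative to complete pairs is

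ratio = [(1 − ρ) × m/n + (1 + ρ)] / 2, with m/n = 16/18 = 0.889.

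- ρ = 0.3: (0.622 + 1.3)/2 = 0.961
- ρ = 0.5: (0.444 + 1.5)/2 = 0.972
- ρ = 0.7: (0.267 + 1.7)/2 = 0.983
- ρ = 0.8: (0.178 + 1.8)/2 = 0.989

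Without the sequence term the ratios are 0.958, 0.970, 0.982 and 0.988. Either way the variance falls by 1 to 4%, and the standard error by about 0.6 to 2%.

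**3. Selection bias in the main crossover analysis.** Assume no true effect, total variance 1, and that the k LEV-first subjects with the worst period-1 within-subject deviations leave before Day 29 and are excluded. ANOVA on treatment alone averages the LEV minus placebo differences over 36 − k pairs, so

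bias = √(1 − ρ) × S_k / (36 − k),

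where S_k is the expected sum, in absolute value, of the k lowest of 18 standard normal values: 1.82, 3.17 and 4.23 for k = 1, 2 and 3. At ρ = 0.7, √0.3 = 0.548:

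- k = 1: 0.548 × 1.82/35 = 0.03 SD
- k = 2: 0.548 × 3.17/34 = 0.05 SD
- k = 3: 0.548 × 4.23/33 = 0.07 SD

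Simulated two-sided type I error is about 6%, 7% and 9%. The same formula gives 0.02 to 0.06 SD at ρ = 0.8 and 0.04 to 0.11 SD at ρ = 0.3.

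**4. Selection bias in the period-1 fallback.** Here the first 4 weeks are compared between sequences. If the lowest scorers on LEV are the ones lost, the LEV mean rises by S_k/(18 − k): 3.17/16 = 0.20 SD for 2 lost and 4.23/15 = 0.28 SD for 3 lost. The large-population formula φ(z_p)/(1 − p) gives 0.213 and 0.300. Simulated type I error of a two-group t test is about 7%, 10% and 15% for 1, 2 and 3 lost.

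**5. The open model choice.** With 4 of 36 period-1-only subjects missing at random, the two estimates correlate at 0.98 to 0.99. Taking whichever result is significant gives about 5.4 to 6.0% type I error.

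**The case against.** The strongest reply concerns size. A reader might infer that the primary result could be wrong by 0.2 to 0.3 SD, against a planned effect of 2 × 0.356 = 0.71 SD. The documents do not support that. The larger shifts belong to the fallback, which is used only if carryover is observed. Section 1.2 gives a half-life of 6 to 8 hours, so the 4-week washout (672 hours) spans 84 to 112 half-lives, and pharmacological carryover is unlikely. Nor do the documents state 0.71 SD: section 10.1 does not say what kind of effect size 0.356 is, and doubling it relies on reading it as Cohen's f.

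The scenarios are also stacked. Ten percent is 3 to 4 subjects in the whole trial. Losing 3 of 18 puts nearly all of them in one sequence, before Day 29, and makes them the worst responders. Section 1.2 describes LEV as well tolerated. That makes heavy treatment-related stopping unsupported, though it does not exclude it.

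A reader might also infer that the plan orders one-period subjects to be deleted, or that withdrawal scores are routinely thrown away. Neither is stated. The first is a property of repeated-measures ANOVA, and section 10.2 acknowledges that the framework has constraints. On the second, withdrawal evaluations are done only where feasible, and Appendix B has no early-termination visit, so some scores will never exist.

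What stands after all this: entry depends on completing treatment, the default test does not use subjects the rule admits, and the trigger for the mixed model is undefined.

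**Conclusion.** The point holds at modest size. The plan conditions the efficacy set on a post-randomisation event that treatment can affect, and it pairs an inclusive rule for period-1 subjects with a default test that cannot use them.

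Lost precision is minor, 1 to 4% of variance at the planned dropout, so the main reasons to change are selection bias and pre-specification. For the main crossover analysis the bias is about 0.03 to 0.07 SD. This assumes a correlation of 0.7 and that the 1 to 3 early leavers are the worst LEV-first responders, so it illustrates an adverse case and is not a forecast. About 0.2 to 0.3 SD applies only to the carryover fallback, with 2 or 3 such leavers. Choosing the model late adds at most about one percentage point to the type I error in the case examined.

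The change is worth making because it is specific and inexpensive, and because the power calculation has little reserve.

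**What to change.** - Analyse all randomised subjects by assigned sequence, using every available post-dose outcome whether or not treatment was completed.
- Make a linear mixed model with treatment, period, sequence and a random subject effect the primary analysis from the start. Delete the switch that depends on dropout being large.
- Assign any withdrawal evaluation to the period in which it occurs.
- State the missing-at-random assumption. Needing a post-dose outcome is itself a post-randomisation condition, and the model cannot repair leaving that depends on unobserved poor response. Therefore report randomised subjects without post-dose data by sequence, and add a simple sensitivity analysis for them.
- Leave the biomarker exclusion as its own stated rule.
- Keep the 4-week-completer ANOVA as a sensitivity analysis.

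The cost is a wording amendment, which needs IRB/IEC approval under sections 13.3 and 15, and possibly slight dilution of the estimate from subjects with short exposure. No additional subjects or visits are needed, and section 10.2 already names the mixed model.
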